9.1 Routine adverse event reporting

Adverse event data collection and reporting, which are required as part of every clinical trial are done to ensure the safety of patients enrolled in the studies as well as those who will enroll in future studies using similar agents. Adverse events are reported in a routine manner at scheduled times according to the study calendar in Section 5.0. For this trial, the Adverse Events: Solicited and Adverse Events: Other forms are used for routine AE reporting in Rave.

Solicited Adverse Events: The following adverse events are considered "expected" and their presence/absence should be solicited, and severity graded, at baseline and for each cycle of treatment. Please note that diarrhea will be graded at baseline based on recording number of stools per day.

CTCAE v4.0 Term	CTCAE v4.0 System Organ Class (SOC)
Fatigue	General disorders
Hot Flashes	Vascular disorders
Diarrhea	Gastrointestinal disorders
Hypertension	Vascular disorders
Dizziness	Nervous system disorders
Seizures	Nervous system disorders
Localized Edema	General disorders
Gynecomastia	Reproductive system and breast disorders
Breast pain	Reproductive system and breast disorders
Weight loss	Investigations

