9.2 CTCAE Routine Reporting Requirements

In addition to the solicited adverse events listed in Section 9.1, the following table outlines the combinations of time points, grades and attributions of AEs that require routine reporting to the Alliance Statistics and Data Center. Questions about routine reporting should be directed to the Data Manager.

*Combinations of CTCAE Grade & Attribution Required for Routine AE Data Submission on Case Report Forms (CRFs)

Attribution	Grade 1	Grade 2	Grade 3	Grade 4	Grade 5
Unrelated			a	a	a
Unlikely			a	a	a
Possible		a	a, b	a, b	a, b
Probable		a	a, b	a, b	a, b
Definite		a	a, b	a, b	a, b

- a) Adverse Events: Other CRF Applies to AEs occurring between registration and within 30 days of the patient's last treatment date, or as part of the Clinical Follow-Up Phase.
- b) Adverse Events: Late CRF Applies to AEs occurring greater than 30 days after the patient's last treatment date.

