Enzalutamide is a strong CYP3A4 inducer and moderate CYP2C9 and CYP2C19 inducer. Enzalutamide reduced plasma exposure of midazolam (CYP3A4 substrate), warfarin (CYP2C9 substrate), and omeprazole (CYP2C19 substrate). Concomitant use of enzalutamide with narrow therapeutic index drugs that are metabolized by CYP3A4 (e.g. alfentanil, cyclosporine, dihydroergotamine, ergotamine, fentanyl, pimozide, quinidine, sirolimus, and tacrolimus), CYP2C9 (e.g. phenytoin, warfarin), and CYP2C19 (e.g. S-mephenytoin) should be avoided, as enzalutamide may decrease their exposure. If co-administration with warfarin cannot be avoided, conduct additional INR monitoring.

Pharmacokinetics

Absorption: rapid with time to peak concentration in 1 hour (range 0.5-3 hours). A high-fat meal did not alter the AUC to enzalutamide or N-desmethyl enzalutamide.

Distribution: 110 L; protein binding of parent drug is 97-98% to primarily albumin; protein binding of active metabolite is 95% to plasma proteins

Metabolism: Hepatic via CYP2C8 (formation of active metabolite N-desmethyl enzalutamide) and CYP3A4

Excretion: Primarily eliminated by hepatic metabolism. Following single oral administration of 14C-enzalutamide 160 mg, 85% of the radioactivity is recovered by 77 days post dose: Urine (71%), feces (14%) primarily as inactive metabolite

T1/2: Enzalutamide: 5.8 days (range 2.8-10.2 days); N-desmethyl enzalutamide: 7.8-8.6 days.

Adverse Events

Common known potential toxicities, > 10%:

Cardiovascular: Peripheral edema, hypertension

Central Nervous System: Fatigue, falling, headache, dizziness

Endocrine & Metabolic: Hot flash, weight loss

Gastrointestinal: Constipation, diarrhea, decreased appetite

Hematologic & Oncologic: Neutropenia

Neuromuscular & Skeletal: Weakness, back pain, arthralgia, musculoskeletal pain

Respiratory: Upper respiratory tract infection, dyspnea

Less common known potential toxicities, 1 to 10%:

Central Nervous System: Myasthenia, insomnia, anxiety, paresthesia, cauda equine syndrome, spinal cord compression, altered mental status, hypoesthesia, hallucination, and restless leg syndrome

Dermatologic: Pruritus, xeroderma

Endocrine & Metabolic: Gynecomastia

Gastrointestinal: Dysgeusia

Genitourinary: Hematuria, pollakiuria

Hematologic & Oncologic: Thrombocytopenia

Hepatic: Increased serum bilirubin

Infection: Infection

Neuromuscular & Skeletal: Bone fracture, stiffness Respiratory: Lower respiratory tract infection, epistaxis

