13.3 Secondary Endpoints

The following endpoints will be evaluated: progression-free survival, overall survival, and adverse events.

Progression-Free Survival: Progression-free survival (PFS) is defined as the time from study entry to the first of either disease progression or death from any cause, where disease progression will be determined based on RECIST 1.1 criteria. PFS will be estimated using the Kaplan-Meier method. The median PFS and 95% confidence interval will be reported.

Overall Survival (OS): OS is defined as the time from study entry to death from any cause. OS will be estimated using the Kaplan-Meier method. The median OS and 95% confidence interval will be reported.

Adverse events: The maximum grade for each type of adverse event will be summarized using CTCAE version 4.0. The frequency and percentage of grade 3+ adverse events will be summarized. We will also closely monitor adverse events throughout the study.

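### The maximum-grade summary in 13.3 covers every adverse-event type at every grade, but outside ten solicited terms 9.2 does not require grade 1, or unrelated or unlikely grade 2, events to be reported

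*Combined protocol and SAP*

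**What the plan says.** Section 13.3 (Secondary Endpoints) plans two adverse-event summaries. The first is "The maximum grade for each type of adverse event will be summarized using CTCAE version 4.0". The second is "The frequency and percentage of grade 3+ adverse events will be summarized". Because the second is already confined to grade 3 and above, the first is naturally read as covering lower grades too.

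Data collection has two routes:

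- **Solicited terms (9.1).** Ten terms are listed: fatigue, hot flashes, diarrhea, hypertension, dizziness, seizures, localized edema, gynecomastia, breast pain and weight loss. For these, "their presence/absence should be solicited, and severity graded, at baseline and for each cycle of treatment".
- **All other terms (9.2).** A grade-by-attribution table sets out the "combinations of time points, grades and attributions of AEs that require routine reporting". Its main form "Applies to AEs occurring between registration and within 30 days of the patient's last treatment date"; a separate form takes later events.

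Section 10.1 lists the toxicities known to occur in more than 10% of patients. One of its lines reads "Neuromuscular & Skeletal: Weakness, back pain, arthralgia, musculoskeletal pain", and none of those four terms is solicited.

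Safety and tolerability are secondary objective 2.2.3.

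**The concern.** The analysis section asks for more than the collection section requires. For an unsolicited term, a patient whose worst event is grade 1, or is grade 2 and judged unrelated or unlikely, need not have a record. Section 13.3 does not acknowledge this and does not say how such a patient is classed.

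Two consequences follow if low-grade rows or any-grade percentages are produced for all terms together. The figures for unsolicited terms can only be too low. The solicited terms will also look relatively more frequent because of how they were collected.

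This bears on objective 2.2.3. Treatment is daily until progression, so persistent mild events are part of tolerability. Section 1.3 also gives possibly better tolerability as one reason for using enzalutamide without castration.

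**Working it through.** The plan gives no figure to reproduce. The check is a reading of the tables followed by an illustration.

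**Step 1: what 9.2 requires.** The table has 5 attributions × 5 grades = 25 cells.

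- Grade 1: 0 of 5 cells required.
- Grade 2: 3 of 5 required (possible, probable, definite).
- Grades 3 to 5: 15 of 15 required on the main form.
- Not required: 5 + 2 = 7 of 25 cells, all at grade 1 or 2.

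The late form, for events more than 30 days after last treatment, covers only grades 3 to 5 that are at least possibly related. The main form's footnote also mentions a clinical follow-up phase, which the section does not define.

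**Step 2: which common toxicities are affected.** The list in 10.1 at more than 10% has 2 cardiovascular + 4 nervous system + 2 endocrine/metabolic + 3 gastrointestinal + 1 hematologic + 4 musculoskeletal + 2 respiratory = 18 terms.

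- Exact matches to a solicited term: fatigue, hot flash, diarrhea, hypertension, dizziness, weight loss = 6.
- Matches if peripheral edema is equated with localized edema: 7.
- Unsolicited: 18 − 7 = 11 (61%) or 18 − 6 = 12 (67%).

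The 11 are falling, headache, constipation, decreased appetite, neutropenia, weakness, back pain, arthralgia, musculoskeletal pain, upper respiratory infection and dyspnea.

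**Step 3: possible size.** The documents give neither a grade split nor the share of grade 2 events called related, so both are assumed. For an unsolicited term, with each patient counted at worst grade:

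recorded rate = P(grade 3+) + P(grade 2) × s

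Here s is the share of grade 2 events judged at least possibly related. True any-grade incidence is set at 20%.

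| Assumed split (grade 1 / 2 / 3+) | s = 25% | s = 50% | s = 100% |
|---|---|---|---|
| 12% / 6% / 2% | 2 + 1.5 = 3.5% (20/3.5 = 5.7-fold) | 2 + 3 = 5% (4.0-fold) | 2 + 6 = 8% (2.5-fold) |
| 5% / 10% / 5% | 5 + 2.5 = 7.5% (2.7-fold) | 5 + 5 = 10% (2.0-fold) | 5 + 10 = 15% (1.3-fold) |

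In the 41 evaluable patients of 13.5, the true count would be 41 × 0.20 = 8.2. The recorded count would lie between 41 × 0.035 = 1.4 and 41 × 0.15 = 6.2. These six cases are illustrations and not bounds: if 90% of affected patients had a non-reportable worst grade, 0.8 of 8.2 would be recorded.

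**Step 4: what is not affected.** All 15 cells at grades 3 to 5 are required up to 30 days after last treatment, so the grade 3+ summary loses nothing in that window. The stopping rule in 13.8 uses treatment-related deaths and seizures. Deaths are grade 5, and seizures are a solicited term.

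**Step 5: a conflict between sections.** The exclusion list in 9.3.1 sends grade 1 to 3 nausea or vomiting, and grade 1 to 3 edema, to routine reporting. Nausea and vomiting are not solicited, and only localized edema is. This does not match the 9.2 table, which requires no unsolicited grade 1 event.

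**The case against.** The case for leaving the plan alone has four parts.

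- **Threshold collection is a deliberate and reasonable way to limit burden.** This stands. The defect is only that 13.3 is written as if all grades were collected for all terms.
- **Among events attributed to the drug, only grade 1 is lost.** This also stands: at least possibly related grade 2 events are all required. However, a single-arm trial has no control group against which to check attribution, and a maximum-grade summary without an attribution limit still lacks the other grade 2 events.
- **The trial plans no tolerability comparison.** True. Efficacy is its main purpose, and two of the symptoms of castration named in 1.3, fatigue and hot flashes, are solicited. This limits the consequence but does not make the unsolicited low-grade figures usable.
- **Any fold figure depends on the assumed split.** True, which is why two splits are shown.

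A reader might also infer that patients with unrecorded events will be counted as having none. The documents do not say so. Section 13.3 defines no row for absent events and no any-grade percentage, and it is silent on patients without a record. A reader might equally infer that no grade 1 event is collected outside the ten terms. That too goes further than the text: 9.2 states what is required and does not forbid more, and 9.3.1 directs some low-grade unsolicited events to routine reporting. Uneven entry of this kind would still not give an interpretable any-grade rate.

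**Conclusion.** The mismatch holds. As written, 13.3 calls for a maximum-grade summary that the data required by 9.2 cannot support for unsolicited terms, and these include 11 or 12 of the 18 toxicities listed at more than 10%. Low-grade or any-grade frequencies for them would be biased downward and not comparable with the solicited terms.

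The size cannot be computed from the documents. At an assumed 20% true incidence, the understatement runs from about 1.3-fold to 5.7-fold across the two grade splits and three attribution shares shown.

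It would be wrong to conclude that the safety analysis as a whole is compromised. The primary endpoint, the grade 3+ summary within the 30-day window and the stopping rule are untouched. The point matters for what objective 2.2.3 can say about mild and moderate events, and it should be corrected because the correction is cheap.

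**What to change.** Amend 13.3 as follows:

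1. Report maximum grade over all grades only for the ten solicited terms, over the period in which they are solicited (baseline until off treatment, per the Section 5.0 footnote).
2. For all other terms, give a separate table labelled with the 9.2 threshold: grade 3 or higher regardless of attribution, and grade 2 or higher at least possibly related, from registration to 30 days after last treatment. Give no any-grade percentage.
3. Report events after 30 days separately, as grade 3 or higher at least possibly related.
4. Where per-cycle laboratory values are on the case report form, derive laboratory grades from them, neutropenia for example. The study calendar already schedules the blood draws, but the documents do not confirm that the values are entered.
5. Reconcile the 9.3.1 statements on grade 1 to 3 nausea or vomiting and edema with the 9.2 table.

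The cost is a change of wording and one extra table, with no new visits or assessments. The downside is that no all-grade figure is offered for unsolicited symptoms. Extending 9.2 to all grades would supply one, but at the price of more data collection.

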13.4 Translational Studies

Due to the limited sample size in this study, the proposed translational studies are considered exploratory and hypothesis generating. Analyses of biomarkers will be summarized by descriptive statistics, including mean, median and standard deviation for continuous biomarker data and frequency (%) for categorical data. Differences in these biomarkers between responders and non-responders will be compared using Fisher's exact tests for categorical biomarker data and Wilcoxon Rank-Sum tests for continuous biomarker data. In addition, a Cox proportional

hazards model will be used to explore the prognostic relationship for these biomarkers measured at baseline and PFS and OS.

13.5 Total Sample Size

A maximum of 41 evaluable patients will be accrued onto this study unless the study is closed early for excessive toxicity or lack of efficacy. We anticipate accruing an additional 10% of patients to account for ineligibility, cancellation, major treatment violation, or other reasons. Therefore, maximum accrual is 45 patients.

13.6 Expected Accrual and Accrual Duration

The expected accrual during the first 6 months is 1 patient per month as sites are opening the trial, then 2 per month. The total time for study accrual is expected to be around 26 months.

13.7 Anticipated time to study completion

We anticipate that the study will take approximately 36 months to complete. This allows a 6-month follow-up for the final patient enrolled, along with data entry, data clean-up, and analysis.

13.8 AE Stopping Rule

The stopping rule specified below is based on the knowledge available at study development. We note that the Adverse Event Stopping Rule may be adjusted in the event of either (1) the study re-opening to accrual after any temporary suspension or (2) at any time during the conduct of the trial and in consideration of newly acquired information regarding the adverse event profile of the treatment(s) under investigation. The study team may also choose to suspend accrual because of unexpected adverse event profiles that have not crossed the specified rule below

The study team will have regular toxicity calls to review overall toxicity, along with AERs reports.

Accrual will be temporarily suspended to this study if at any time we observe events considered at least possibly related to study treatment (i.e., an adverse event with attribute specified as "possible", "probable", or "definite") that satisfy the following criteria.

• For this study, unacceptable toxicity is defined as: treatment related deaths or seizures. If 1 or more patients out of the first 10 patients enrolled (or subsequently, if more than 10% of all patients) develop unacceptable toxicity, the study will be temporarily suspended until the review of all toxicity data is completed and a decision is made about whether it is safe to resume accrual. This decision will be made by consensus of the study team and CTEP.

In addition, any required reporting to the FDA will be made as per 21 CFR 312.32 by the pharmacovigilance executive officer and Alliance regulatory department.

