- *** The hormone panel includes total and free testosterone. The hormone panel will be drawn first after study registration but PRIOR to initiation of study drug, and then Day 1 of every even-numbered cycle starting with cycle 2 times 3 (D1C2, D1C4, D1C6, +/- 7 days), and then at off study (+/- 7 days).
- Ψ To be completed after registration and ≤ 21 days prior to treatment, see Section 1.5 and Appendix I.
- π Solicited AEs are to be collected starting at baseline until off treatment (See Section 9.1). Routine AEs are to be collected starting after registration. See Section 9.3 for expedited reporting of SAEs.
- # At baseline (after registration and prior to day 1 cycle 1 of study drug) and after progression (See Section 6.2 for further information).
- Medication diary should be completed by the patient throughout treatment, and should be collected by site staff at day 1 of every cycle starting with day 1 cycle 2. See Appendix II.
- For women of childbearing potential (see Section 3.3). Must be done ≤ 5 days prior to registration and ≤ 10 days prior to day 1 cycle 1.
- 3 See Sections 6.2.
- 4 Baseline scans can include either: 1) a CT, spiral CT, or MRI, or 2) an FDG-PET scan and diagnostic CT performed with both IV and oral contrast, with the CT acquired with 5 mm or less slice thickness (see Section 11.3.2). Supporting documentation is to be submitted, per Section 6.1.1.
- 5 For patients who consent to submitting archival tumor tissue and research blood samples for correlative tissue analyses and banking, these should be obtained and submitted within 30 days of registration.
- A Every 2 cycles for the first 8 cycles (beginning Day 1 Cycle 3) then every 3 cycles (beginning with Day 1 Cycle 9), until evidence of progression or relapse. Confirmatory scans should also be obtained at least 4 weeks following documentation of objective response (see Section 11.0). Response assessment should include assessment of all sites of disease and use the same imaging method as was used at baseline.

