Resulting in Hospitalization ≥ 24 hrs	10 Calendar Days	- 24-Hour 5 Calendar Days
Not resulting in Hospitalization ≥ 24 hrs	Not required	

Expedited AE reporting timelines are defined as:

- o "24-Hour; 5 Calendar Days" The AE must initially be reported via-CTEP-AERS within 24 hours of learning of the AE, followed by a complete expedited report within 5 calendar days of the initial 24-hour report.
- o "10 Calendar Days" A complete expedited report on the AE must be submitted within 10 calendar days of learning of the AE.

¹Serious adverse events that occur more than 30 days after the last administration of investigational agent/intervention and have an attribution of possible, probable, or definite require reporting as follows:

Expedited 24-hour notification followed by complete report within 5 calendar days for:

• All Grade 3, 4, and Grade 5 AEs

Expedited 10 calendar day reports for:

- Grade 2 AEs resulting in hospitalization or prolongation of hospitalization
- Expedited AE reporting timelines defined:
 - "24 hours; 5 calendar days" The investigator must initially report the AE via CTEP-AERS ≤ 24 hours of learning of the event followed by a complete CTEP-AERS report ≤ 5 calendar days of the initial 24-hour report.
 - "10 calendar days" A complete CTEP-AERS report on the AE must be submitted $\leq \underline{10}$ calendar days of the investigator learning of the event.
- Any medical event equivalent to CTCAE grade 3, 4, or 5 that precipitates hospitalization (or
 prolongation of existing hospitalization) must be reported regardless of attribution and
 designation as expected or unexpected with the exception of any events identified as protocolspecific expedited adverse event reporting exclusions (see below).
- Use the NCI protocol number and the protocol-specific patient ID provided during trial registration on all reports.

Additional Instructions or Exclusion to CTEP-AERS Expedited Reporting Requirements for Phase 2 and 3 Trials Utilizing an Agent Under a CTEP IND or non-CTEP IND:

- All adverse events reported via CTEP-AERS (i.e., serious adverse events) should also be forwarded to your local IRB.
- Grade 3/4 hematosuppression and hospitalization resulting from such do not require CTEP-AERS, but should be submitted as part of study results.
- Grade 1-3 nausea or vomiting and hospitalization resulting from such do not require AERS reporting, but should be reported via routine AE reporting

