- Grade 3 or 4 nausea or vomiting does not require AERS reporting, but should be reported via routine AE reporting.
- Grade 1-3 diarrhea and hospitalization resulting from such do not require AERS reporting, but should be reported via routine AE reporting
- Grade 3 or 4 diarrhea does not require AERS reporting, but should be reported via routine AE reporting.
- Grade 1-3 fatigue and hospitalization resulting from such do not require AERS reporting, but should be reported via routine AE reporting
- Grade 3 or 4 fatigue does not require AERS reporting, but should be reported via routine AE reporting.
- Grade 1-3 hot flashes and hospitalization resulting from such do not require AERS reporting, but should be reported via routine AE reporting
- Grade 3 or 4 hot flashes does not require AERS reporting, but should be reported via routine AE reporting.
- Grade 1-3 edema and hospitalization resulting from such do not require AERS reporting, but should be reported via routine AE reporting
- Grade 3 or 4 edema does not require AERS reporting, but should be reported via routine AE reporting.
- Grade 2 or greater posterior reversible leukoencephalopathy syndrome must be reported via AERS.
- All new malignancies must be reported via CTEP-AERS whether or not they are thought to be related to either previous or current treatment. All new malignancies should be reported, i.e. solid tumors (including non-melanoma skin malignancies), hematologic malignancies, myelodysplastic syndrome/acute myelogenous leukemia, and in situ tumors. In CTCAE v5.0, secondary malignancies may be reported as one of the following three options: 1) Leukemia secondary to oncology chemotherapy, 2) Myelodysplastic syndrome, or 3) Treatment-related secondary malignancy. Whenever possible, the CTEP-AERS reports for new malignancies should include tumor pathology, history or prior tumors, prior treatment/current treatment including duration, any associated risk factors or evidence regarding how long the new malignancy may have been present, when and how the new malignancy was detected, molecular characterization or cytogenetics of the original tumor (if available) and of any new tumor, and new malignancy treatment and outcome, if available.
- Treatment expected adverse events include those listed in Section 10.0 and in the package insert.
- CTEP-AERS reports should be submitted electronically.

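### One low-grade seizure can suspend accrual under Section 13.8, yet Section 9.3.1 sets no expedited deadline for telling the study team about it

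*Combined protocol and SAP*

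**What the plan says.** **The rule.** Section 13.8 acts on two kinds of event: "unacceptable toxicity is defined as: treatment related deaths or seizures". The threshold is "If 1 or more patients out of the first 10 patients enrolled (or subsequently, if more than 10% of all patients) develop unacceptable toxicity". Timing and attribution are set by "Accrual will be temporarily suspended to this study if at any time we observe events considered at least possibly related to study treatment". No seizure grade is excluded. The same section adds "The study team will have regular toxicity calls to review overall toxicity, along with AERs reports", without giving a call frequency.

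**Expedited reporting.** The Section 9.3.1 table sets deadlines by grade and hospital stay. Grade 3-5 events need notice within 24 hours of the site learning of them and a full report within 5 calendar days. Grade 1-2 events with a stay of 24 hours or more have 10 calendar days. In the row "Not resulting in Hospitalization ≥ 24 hrs", the grade 1-2 entry is that no report is needed. The protocol-specific instructions add one neurologic event, "Grade 2 or greater posterior reversible leukoencephalopathy syndrome must be reported via AERS", and do not mention seizure.

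**Routine reporting.** Section 9.1 lists seizures among the solicited events, to be graded at baseline and each cycle, and says "Adverse events are reported in a routine manner at scheduled times according to the study calendar". The Section 5.0 footnote adds "Solicited AEs are to be collected starting at baseline until off treatment". The Section 9.2 table for other events takes nothing at grade 1. It takes grade 2 only when attribution is at least possible.

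**The concern.** A rule that turns on one patient works only if that event reaches the people who apply it. Section 13.8 treats a seizure of any grade as enough to pause accrual early in the trial. Section 9.3.1 treats a low-grade seizure without a 24-hour stay as an event that can wait for the routine forms. The sponsor did tailor the expedited list for one neurologic risk, but not for the one that drives its own suspension rule.

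Two things are at stake. Patients may be enrolled after the event that should have paused accrual. And the seizure count used for safety objective 2.2.3 may omit a grade 1 event that occurs after treatment ends.

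**Working it through.** **1. Route of a treatment-related grade 1-2 seizure, on treatment, no 24-hour stay, already known to the site**

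| Step | Source | Result |
|---|---|---|
| Does it count toward suspension? | 13.8 | Yes, at any grade |
| Expedited report by the table? | 9.3.1 table | None required |
| Protocol-specific override? | 9.3.1 additional instructions | None for seizure |
| Covered as an important medical event? | 9.3.1, item 6 | Only by medical judgement, and the timeframe then refers back to the same table |
| Routine form? | 9.1, 5.0 | Yes, at a scheduled or removal visit |
| Toxicity calls? | 13.8 | Yes, frequency not stated |

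A note in 9.3.1 asks for immediate reporting of any serious event. The text after it ties reporting to the table's timeframes, and the table asks for nothing here. A site could follow either reading.

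**2. Accrual, to size a delay**

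Inputs from 13.5 and 13.6: at most 45 patients; 1 per month for 6 months, then 2 per month.

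- Plan's own figure: 6 + (45 − 6)/2 = 25.5 months, which agrees with the stated figure of around 26.
- Tenth patient: 6 + (10 − 6)/2 = month 8. Accrual is therefore 1-2 per month while the one-patient threshold applies.

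Patients enrolled during a delay of D days, counted from when the site learns of the event, are D/30.44 × monthly rate. The documents give no D for this event, so the rows below are illustrations:

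| D | At 1 per month | At 2 per month |
|---|---|---|
| 1 day (the 24-hour notice) | 0.03 | 0.07 |
| 10 days (the deadline for a hospitalised grade 1-2 event) | 0.33 | 0.66 |
| 30.44 days (one month) | 1.0 | 2.0 |

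Each month of delay adds about 1-2 patients, which is 10-20% of the first 10.

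**3. How often this could arise**

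Section 10.1 lists seizure below 1%. Taking 1% as an assumed upper bound that carries over to this population, the chance of any seizure in 10 patients is at most 1 − 0.99^10 = 9.6%. The gap concerns only the part of these that is low-grade, without a 24-hour stay and at least possibly related. After the tenth patient the rule needs more than 10% of all patients (2 of 11, 3 of 20), so a single late report matters less.

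**4. After treatment ends**

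- Solicited collection has stopped (5.0 footnote).
- Section 9.2 takes grade 2 if at least possibly related, and grade 3-5 always, up to 30 days after the last treatment. It does not take grade 1.
- The calendar marks an adverse event assessment at removal and requires an evaluation 30 days after treatment, but no form is required to take a grade 1 seizure found there.

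**The case against.** The strongest reply is that the protocol has other ways to notice a seizure. Section 8.2.2 stops study drug for any seizure, so a known event leads to the removal assessment in the study calendar. It need not wait for the next cycle visit. The toxicity calls review all toxicity, not only AERS reports. A site may also judge the event important enough to report at once, and the team may suspend accrual at its discretion for an unexpected adverse event profile. Seizure is rare, and patients with a seizure history or brain metastases are excluded by 3.3.7.

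Most of this stands, and it limits the size of the point. It does not remove the mismatch. The removal assessment produces a routine form with no submission deadline in these documents. The calls have no stated interval. The judgement clause leads back to a table that asks for nothing. Discretionary suspension is not the rule, and Section 9.1 classes seizure as expected.

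A reader might go further and infer from the 28-day cycle that the rule would act about a cycle late, and that a 24-hour AERS line would recover all of that time. The documents do not support this. The AERS clock starts when the site learns of the event, so it cannot shorten a wait before that. A known seizure prompts a removal assessment. Form deadlines lie in a Data Submission Schedule that is not part of these documents.

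**Conclusion.** The mismatch between 13.8 and 9.3.1 is in the text. An event that can suspend accrual alone may be known to the site, with the protocol followed exactly, and still have no expedited deadline for reaching the study team. The lag cannot be computed. Its cost is about 1-2 extra patients per month of delay, if accrual runs as planned.

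The point assumes that an outpatient seizure can be graded 1 or 2. The documents do not reproduce the CTCAE criteria, so this cannot be checked here. It also assumes that no site instruction outside these documents closes the gap.

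A reader might also infer that low-grade seizures go missing from the data. That is too strong. On treatment, every grade is solicited. After treatment, grade 2 events at least possibly related and all grade 3-5 events are taken up to 30 days. What remains is a grade 1 seizure after treatment ends, which has no required form entry.

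Severity is low. This is a cheap improvement to a safety rule. It does not affect the primary analysis.

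**What to change.** Three short changes to reporting, none of which alters a dose or a clinical rule:

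1. In the additional instructions of 9.3.1, state that any seizure, of any grade and regardless of hospitalization, through 30 days after the last dose, is reported via CTEP-AERS within 24 hours of the site learning of it.
2. In 9.1 and the Section 5.0 footnote on solicited events, continue the seizure item through the 30-day post-treatment evaluation that the calendar already requires.
3. In 13.8, state that these reports feed the suspension rule in addition to the solicited forms and toxicity calls. AERS should not be named as the only source, because that would narrow a rule meant to act on whatever the team observes. The requirement of at least possible attribution stays as it is.

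The cost is a few sentences in an amendment and a few extra expedited reports, given that 10.1 lists seizure below 1%. No visit is added.
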